## **Appendix A: Heart Failure Hospitalization, Emergency Room visit for heart failure and urgent outpatient clinic visit**

**Heart Failure (HF) Hospitalization** is defined as an event that meets ALL of the following criteria:

1. The patient is admitted to the hospital with a primary diagnosis of heart failure
2. The patient exhibits new or worsening HF symptoms, including at least ONE of the following:
  - a) Dyspnea (dyspnea at rest, orthopnea, paroxysmal nocturnal dyspnea)
  - b) Decreased exercise tolerance
  - c) Fatigue
  - d) Other symptoms of worsened end-organ perfusion or volume overload
3. The patient has objective evidence worsening heart failure, consisting of at least TWO physical examination findings OR one physical examination finding and at least ONE laboratory criterion), including:
  1. Physical examination findings:
    - a) Peripheral edema
    - b) Increasing abdominal distention or ascites
    - c) Pulmonary rales/crackles/crepitations
    - d) Increased jugular venous pressure and/or hepatojugular reflux
    - e) S3 gallop
    - f) Clinically significant weight gain thought to be related to fluid retention
  2. Laboratory evidence of heart failure, including:
    - a) Increased N-terminal pro-BNP (NT- proBNP) or B-type natriuretic peptide (BNP) concentrations consistent with decompensation of heart failure.
    - b) Radiological evidence of pulmonary congestion
    - c) Non-invasive or invasive diagnostic evidence of clinically significant elevated left- or right-sided ventricular filling pressure or low cardiac output by echocardiogram report.
    - d) The patient receives initiation or intensification of treatment specifically for heart failure, including at least ONE of the following:
      - a. Augmentation in oral diuretic therapy
      - b. Intravenous diuretic, inotrope, or vasodilator therapy
      - c. Mechanical or surgical intervention, including: Mechanical circulatory support (e.g., intra-aortic balloon pump, ventricular assist device) or Mechanical fluid removal (e.g., ultrafiltration, hemofiltration, dialysis)

**Emergency Room Visit for Heart Failure:** defined as an event that meets all of the following:

1. Unscheduled visit to the Emergency Department (ED) with worsening symptoms and with a primary diagnosis of heart failure, with intensified HF treatment but not requiring HF hospitalization.
2. The patient exhibits new or worsening symptoms due to heart failure as described above, including at least ONE of the following:
  - a) dyspnea (dyspnea at rest, orthopnea, paroxysmal nocturnal dyspnea),
  - b) decreased exercise tolerance, increasing fatigue,

- c) symptoms of worsened end-organ perfusion or volume overload
- 3. The patient has objective evidence worsening heart failure, with at least TWO physical examination findings OR one physical examination finding and ONE laboratory criterion):

A) Physical examination findings:

- 2. Peripheral edema
- 3. Increasing abdominal distention or ascites
- 4. Pulmonary rales/crackles/crepitations
- 5. Increased jugular venous pressure and/or hepatojugular reflux
- 6. S3 gallop
- 7. Clinically significant weight gain thought to be related to fluid retention

B) Laboratory evidence of heart failure, including:

- 1. Increased N-terminal pro-BNP (NT- proBNP) or B-type natriuretic peptide (BNP) concentrations consistent with decompensation of heart failure.
- 2. Radiological evidence of pulmonary congestion
- 3. Non-invasive or invasive diagnostic evidence of clinically significant elevated left- or right-sided ventricular filling pressure or low cardiac output by echocardiogram report.
- 4. The patient receives initiation or intensification of treatment specifically for heart failure, including at least ONE of the following:
  - 1. Augmentation in oral diuretic therapy
  - 2. Intravenous diuretic, inotrope, or vasodilator therapy
  - 3. Mechanical or surgical intervention, including: Mechanical circulatory support (e.g., intra-aortic balloon pump, ventricular assist device) or Mechanical fluid removal (e.g., ultrafiltration, hemofiltration, dialysis)

**Urgent Heart Failure Visit:** defined as an event that meets all of the following:

- 1. The patient has an urgent, unscheduled office/practice or emergency department visit for a primary diagnosis of heart failure, but not meeting the criteria for a heart failure hospitalization.
- 2. All signs and symptoms for heart failure hospitalization (i.e., a) symptoms; b) physical examination findings/laboratory evidence of new or worsening heart failure, as indicated above)
- 3. The patient receives initiation or intensification of treatment specifically for heart failure, as detailed in the above section with the exception of oral diuretic therapy, which will not be sufficient.

## Appendix B: COVID-19

On March 11, 2020, the World Health Organization declared the 2019 novel coronavirus – and COVID-19, disease caused by the virus – a global pandemic. In response, efforts to contain the spread of COVID-19 have been implemented across the United States and have impacted the conduct of clinical research trials. In an effort to maintain, as much as possible, the integrity of the DAPA HF on Hospital Readmission trial so that the data can be used to answer the questions that the trial intended, certain adjustments in visit procedures may be considered on a case-by-case basis, as outlined below. Emory University should be notified before making these adjustments.

- **Screening/randomization Visit (Visit S/R) – hospital admission:**
  - Screening/randomization activities may be suspended at sites until such time that it is considered appropriate by the site to resume activities
- **Visit 2 (Week 2) - office visit:**
  - This visit can be conducted at 2 weeks or less. This visit is usually conducted at the same time participant has been scheduled for follow up with heart failure services after hospital discharge.
- **Visit 3 (Week 6), 7 (Week 20) - office visit:**
  - an office visit is preferred
  - The visit could be delayed and the visit window extended to accommodate an office visit
  - Conducting the visit by phone could be considered
  - If conducted by phone, complete the phone visit procedures outlined in the **Schedule of Assessments** on page 9
  - If laboratory collection is needed at investigator's discretion, please mail/email study laboratory requisition for participant to choose a convenient LabCorp location
- **Visit 4 (Week 8), 6 (Week 16), and 8 (Week 24) - phone visits:**
  - Conduct visits, as scheduled, by phone
- **Visit 5 (Week 12) - office visit:**
  - An office visit is needed to collect study endpoints (echocardiogram, laboratories, questionnaires, 6-minute walk test, and dispensing IP)
  - The visit could be delayed and the visit window extended to accommodate an office visit
  - If needed, study drug could potentially be mailed by sites to a patient to keep them on study drug (depending upon local regulations) until such time that the Week 12 visit can be conducted in the office
- **Visit 9 (Week 26) - office visit:**
  - An office visit is needed to collect study endpoints (laboratories, questionnaires, and 6-minute walk test).

The visit could be delayed and the visit window extended to accommodate an office visit

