**Innovation.** The proposed study will be the first prospective RCT to determine the safety and efficacy of dapagliflozin treatment in preventing readmissions/ER visits/urgent clinic visits and death in patients with and without T2D after admission for ADHF. Treatment with SGLT2-i has been shown to reduce both HF hospitalization and mortality in patients with established heart disease and a history of HF . More recently, among patients with HFrEF, dapagliflozin was shown to reduce the risk of worsening heart failure or death from cardiovascular causes compared to placebo, regardless of the presence or absence of diabetes . However, the time of initiation of SGLT2-i therapy has yet to be formally evaluated in patients with ADHF and is the purpose of this study. In addition, we will evaluate the impact of treatment on HF symptoms quality of life, resource utilization and cost-effectiveness of dapagliflozin versus placebo. The results of this study have great potential to influence and facilitate care and to change current clinical guidelines in the management of patients with ADHF.

**Rationale on Dapagliflozin treatment.** Dapagliflozin (Farxiga®) is a highly selective SGLT2-i, given in once-daily doses. It is rapidly absorbed with a time to maximum plasma concentration of two hours and a half-life of 17 hours, with an absolute oral bioavailability of dapagliflozin following the administration of a 10 mg dose of 78%. Dapagliflozin is approximately 91% protein bound. Protein binding is not altered in patients with renal or hepatic impairment. The metabolism of dapagliflozin is primarily mediated by UGT1A9; CYP-mediated metabolism is a minor clearance pathway in humans. Dapagliflozin and related metabolites are mainly eliminated via the renal pathway. The mean plasma terminal half-life for dapagliflozin is approximately 12.9 hours following an oral dose of Farxiga 10 mg.

Clinical trial in ambulatory patients with T2D reported a significant reduction in HbA1c of ~ 0.8%-1.5% from baseline in patients with T2D. Dapagliflozin as monotherapy and in combination with other antidiabetic drugs is well tolerated and associated with very low rates of hypoglycemia. In addition, due to its mechanism of action of increasing urinary glucose excretion, SGLT2-i can reduce systolic blood pressure and body weight compared to placebo in patients with T2D.

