### **Study Endpoints:**

**Primary outcome** is to compare the efficacy of dapagliflozin compared with placebo, on the composite rate of hospital admissions, emergency department visits, urgent clinic visits for HF and death after admission with ADHF.

**Secondary outcomes** are to determine differences between dapagliflozin compared to placebo in:

1. Change in the KCCQ score between baseline score and the scores at 12, and 26 weeks
2. Change in the CHQ-SAS score between baseline score and the scores at 12, and 26 weeks
3. Change in NT proBNP levels between baseline and after 12 and 26 weeks
4. Change in 6-minute walk distance (6MWD) between baseline and after 12 and 26 weeks
5. Change in HbA1c between baseline and after 12 and 26 weeks (in T2D patients). [SEP]
6. Change in weight between baseline and after 12 and 26 weeks [SEP]
7. Change in systolic blood pressure between baseline and after 12 and 26 weeks
8. Change from baseline in left atrial volume index and other measures of left ventricular systolic and diastolic function in patients who may undergo repeated echocardiogram during follow up.

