## 9. Change from baseline in serum magnesium at baseline and after 12 and 26 weeks

### Safety Variables

1. All-cause mortality
2. Cardiovascular death
3. Non-fatal myocardial infarction (MI)
4. Stroke
5. Acute kidney injury (defined as doubling of serum creatinine based on the RIFLE criteria ).
6. Adverse events (AEs) and serious adverse events (SAEs). Of special interest are events including diabetic ketoacidosis (DKA), volume depletion (defined as hypotension, syncope, orthostatic hypotension or dehydration), hypoglycemic events and urinary tract infections.

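### Under the COVID-19 appendix, week-26 laboratories and questionnaires must wait for an office visit that can slip without limit, though five of the eight week-26 secondary endpoints do not need the clinic

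*Combined protocol and SAP*

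**What the plan says.** Appendix B sets visit rules for the COVID-19 emergency. They are applied case by case, and the coordinating university is to be told first.

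- **Visit 9 (week 26):** "An office visit is needed to collect study endpoints (laboratories, questionnaires, and 6-minute walk test"). The next line adds: "The visit could be delayed and the visit window extended to accommodate an office visit". No latest date, remote route or drug-mailing provision is given.
- **Visit 5 (week 12):** the same office-visit rule, plus a provision to mail drug if the visit is late.
- **Visits 3 and 7 (weeks 6 and 20):** an office visit is preferred, but "Conducting the visit by phone could be considered". For laboratories wanted at the investigator's discretion, sites are told: "please mail/email study laboratory requisition for participant to choose a convenient LabCorp location".
- **Visits 4, 6 and 8 (weeks 8, 16 and 24):** "Conduct visits, as scheduled, by phone".

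Study Endpoints lists nine secondary outcomes, for example "Change in NT proBNP levels between baseline and after 12 and 26 weeks" and "Change from baseline in serum magnesium at baseline and after 12 and 26 weeks". Treatment lasts 26 weeks (Duration of treatment), and Schedule of Clinic and Phone Visits ends it at Visit 9, labelled week 26. Neither says what happens to dosing when Visit 9 is late. Three bottles of 35 tablets are dispensed at randomization and again at week 12 (Drug Dispensing Scheme). Unused drug is to be brought to each office visit (Drug Accountability). The normal visit window is seven days either side (Schedule of Assessments, footnotes).

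**The concern.** The rule ties every week-26 secondary endpoint to one physical visit, and during the emergency that visit may be postponed indefinitely. Aim 2 names HbA1c, NT-proBNP, KCCQ and CHQ-SAS at 12 and 26 weeks. All four are blood tests or questionnaires, and so could be obtained without the clinic.

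A value taken well after week 26 is not a week-26 value. It reflects either longer exposure or, once tablets run out, time off drug. Analysis of Secondary Endpoints compares groups at named time points and gives no rule for out-of-window values, so a late value could enter as if on time. If the office visit never takes place, the value is missing. An on-time sample cannot be recovered afterwards.

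**Working it through.** The plan states no figure to reproduce here. The check counts endpoints and sets drug supply against visit timing.

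**1. Endpoints.** Nine secondary outcomes are listed. The echocardiographic one has its protocol scan at week 12, so 9 − 1 = 8 are due at week 26.

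- Laboratory: NT-proBNP, HbA1c (T2D patients), magnesium = 3.
- Questionnaire: KCCQ, CHQ-SAS = 2.
- Clinic measurement: 6-minute walk, weight, systolic blood pressure = 3.

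A late Visit 9 moves all 8. Remote collection could protect 3 + 2 = 5.

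**2. Supply.** Each dispensing is 3 × 35 = 105 tablets. The total is 210, against 26 × 7 = 182 days of treatment. Assume one tablet daily, none missed, from day 0.

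- Leftovers returned at Visit 5: run-out = Visit 5 day + 105. Visit 5 on day 77, 84 or 91 gives day 182, 189 or 196 (week 26, 27 or 28).
- Leftovers kept: run-out = day 210 (week 30).

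If Visit 5 is itself delayed under Appendix B and drug is dispensed or mailed then, run-out moves later.

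**3. Days without drug at a late Visit 9** = visit day − run-out day, floor 0. The delays are illustrative; the documents give none.

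| Visit 9 | Returned, V5 day 77 | Returned, V5 day 84 | Returned, V5 day 91 | Kept |
|---|---|---|---|---|
| Week 28 (day 196) | 14 | 7 | 0 | 0 |
| Week 30 (day 210) | 28 | 21 | 14 | 0 |
| Week 32 (day 224) | 42 | 35 | 28 | 14 |
| Week 34 (day 238) | 56 | 49 | 42 | 28 |

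The day-77 column also describes any patient whose dosing stops at day 182.

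**4. What off drug means.** The drug rationale states: "The mean plasma terminal half-life for dapagliflozin is approximately 12.9 hours following an oral dose of Farxiga 10 mg". It also gives 17 hours. Five half-lives are 5 × 12.9 = 64.5 h (2.7 days) or 5 × 17 = 85 h (3.5 days), leaving 0.5^5 = 3.1% of plasma drug. This concerns plasma drug only. How fast each endpoint drifts back is not in the documents.

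**5. Size.** Let f be the share of patients measured off drug. If the effect is partly or fully lost but not reversed, a mean difference shrinks by between 0 and f. At an assumed f = 10%, that is between 0 and 10%. The documents do not give f.

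**6. The normal window.** Day 182 ± 7 is days 175 to 189. A draw on days 175 to 182 has 0 days off drug in every column above. A draw on day 189 has at most 189 − 182 = 7. The week-24 call falls on day 168 ± 7, days 161 to 175, so even the latest call leaves 189 − 175 = 14 days to arrange a draw.

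**The case against.** The strongest reply is that Appendix B is consistent. It treats the two endpoint visits (5 and 9) alike and reserves phone contact for interim visits. The remote draws at Visits 3 and 7 are discretionary tests, not endpoint samples. Keeping endpoints in the clinic also keeps the questionnaire mode the same as at baseline and week 12. This stands in part: the comparison shows that a remote route exists in the trial, not that the appendix contradicts itself. It does not explain why a blood draw must wait for a walking test.

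Second, a reader might infer that week-26 values will be measured off drug. The documents do not support that. Treatment is tied to Visit 9, and dispensed supply often reaches past week 26. Off-drug measurement needs either a stop at day 182, which no text orders for a late visit, or a delay beyond run-out.

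Third, on-drug timing is not a stated requirement. Premature Treatment Discontinuation asks patients who stop drug to keep attending, and the secondary analyses are not restricted to on-drug values. This too stands. But a value postponed for logistical reasons is still not the week-26 value the endpoint names.

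Fourth, the provision is narrow: case by case, with prior notice, and only in the emergency. That limits the importance of the point but does not remove the gap.

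**Conclusion.** The point holds as a minor, cheaply corrected weakness. As written, Appendix B lets all eight week-26 secondary endpoints be late without limit, or be lost, because three of them need the clinic. Five is the number that remote collection can protect. It would be wrong to read five as the number exposed.

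Off-drug measurement is possible, not established. With Visit 5 in its window, it begins at about weeks 26 to 28 if leftovers are returned, or week 30 if they are kept. This assumes daily dosing with none missed.

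No bias can be quantified, because neither the frequency of late visits nor the rate of drift is given. The primary composite and the week-12 values are outside this point.

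**What to change.** In Appendix B, Visit 9, add in substance:

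- If an office visit within days 175 to 189 is not expected at the week-24 call, or is later cancelled, draw the week-26 laboratories within that window by mailed study requisition, the route already given for Visits 3 and 7. Aim for days 175 to 182 where possible. Use these as the week-26 values in the main analysis.
- KCCQ and CHQ-SAS may be completed by phone or mail in the same window, with mode recorded.
- 6-minute walk, weight and blood pressure follow at the delayed office visit, with the actual visit day and last-dose date recorded.

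Do not pair this with a rule that drug stops at week 26. With an on-time Visit 5, such a rule would raise time off drug at a week-28 visit from 7 days (leftovers returned) or 0 (kept) to 14, and at a week-30 visit from 21 or 0 to 28. That would worsen the three measures still taken in the clinic.

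**Cost.** A few sentences, one requisition and one contact per affected patient, and data fields for mode, visit day and last-dose date. No extra drug is needed. There are two downsides. Remote questionnaire scores may differ from clinic scores by an amount the documents do not give; with blinded 1:1 arms this should add noise more than bias between arms. The requisition is also assumed to be able to cover NT-proBNP, HbA1c and magnesium. The laboratory change is worth making even if the questionnaires stay in the clinic.
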